5.2 TRIAL TREATMENTS

All babies participating in the trial, except those randomised to the control group, will receive chlorhexidine with or without emollient. Treatment should start immediately following randomisation as described below, following the randomised frequency schedule.

5.2.1 CHLORHEXIDINE

Babies will be randomised to three different concentrations of chlorhexidine by dilution, 0.5%, 1% and 2%, to be applied daily (working days s only) or on alternate working days (three times a week) until day 14 after enrolment or discharge from hospital, whichever is earlier. Each baby will be allocated their own labelled bottle of the diluted product.

Before chlorhexidine is applied, the baby's temperature should be measured and the skin condition score assessment should be performed. Keeping the baby warm, treatment should be applied to the whole body (excluding face and eyes) using cotton wool, avoiding pooling of the chlorhexidine around the baby. After the application, the baby should be re-dressed and their body temperature should be measured after 15 minutes. The baby should be observed for skin reactions at 30 minutes after each application.

In the case of rare and highly unlikely accidents such as splash injury to the eye from chlorhexidine, flush the affected area with copious water or saline as quickly as possible, and consider whether referral for an opthalmological assessment is necessary.

5.2.1.1 Dispensing

Chlorhexidine will be diluted in the hospital pharmacy and transported to the ward in pre-defined concentrations. Containers for individual use will be prepared on the ward and labelled for clinical trial use, adding the trial number and date of birth to each container immediately after randomisation. Individual containers should be stored in a central location until application. These containers should not be shared with any other trial participants or babies outside the trial.

5.2.1.2 Dose Interruptions & Discontinuations

Doses and concentrations will not be modified after the baby has been randomised. Consideration of temporary or permanent discontinuation of chlorhexidine should be made at the discretion of the treating clinician in the following circumstances:

- Hypothermia < 36.0C immediately before chlorhexidine application
- Skin score >2 in any category immediately before chlorhexidine application (see Appendix I)
- Neurological disturbance

When chlorhexidine is temporarily stopped for any reason, an assessment will be performed at the time of the next scheduled application and the clinician will determine whether it should be restarted.

Treatment interruptions and discontinuation should be recorded as appropriate on the trial CRFs/worksheets.

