In addition, the skin of the babies will be closely monitored for any signs of side effects to chlorhexidine. Applying an antiseptic can make babies colder and can sometimes cause skin reactions which may make it easier for bacteria to get into the babies instead of protecting them. But we don't know how these different advantages and disadvantages balance out. This study will look at the balance between reducing numbers of bacteria and safety. In the future, we plan to test the best method to reduce the number of bacteria on newborn babies' skin we find in this study in a much larger study, to see whether it could reduce serious infections or not.

TRIAL SCHEMA

Figure 1: Trial Schema

Follow up to 28 days. Last application of CHG at day 14 after enrolment or discharge (whichever earlier)

Co-primary outcome(s)

- Change in bacterial load from baseline to final swab (efficacy)
- Adapted Neonatal Skin Condition Score (safety) (absolute score and grade)

Secondary outcomes

- Temperature (change in absolute temperature and grade (hypothermia))
- Acquisition & loss of specific bacterial species
 - Enterobacteriaceae
 - Acinetobacter
 - Staphylococcus aureus
 - Beta haemolytic streptococci (group A and B)
 - Enterococcus
 - Candida
 - Pseudomonas aeruginosa
- Serious adverse events

Note: CHG=chlorhexidine gluconate. Alternate working days are Monday, Wednesday, Friday; or Tuesday, Thursday, Saturday, depending on the standard working pattern in each country.

Figure 2: Trial Entry, Randomisation and Treatment

*E= Emollient (same timing as CHG) *NoE = No Emollient.

Note: CHG=chlorhexidine gluconate. Alternate working days are Monday, Wednesday, Friday; or Tuesday, Thursday, Saturday, depending on the standard working pattern in each country.

SUMMARY OF TRIAL

SUMMARY INFORMATION TYPE	SUMMARY DETAILS
Short title	NeoCHG
Long title	Efficacy and safety of whole-body chlorhexidine (CHG) cleansing in reducing bacterial skin colonisation of hospitalised low birth weight neonates: A pilot trial
Version	2.0
Date	29-Nov-2021
ISRCTN #	ISRCTN69836999
Study Design	Factorial randomised controlled pilot trial
Setting	Hospital neonatal units in South Africa and Bangladesh
Type of Participants to be Studied	Hospitalised low birth weight (1-2kg) babies between the ages of 1-6 days at enrolment
Ancillary Studies/Sub-studies	None
Sponsor	St George's, University of London

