1.4 CLINICAL EXPERIENCE OF CHLORHEXIDINE IN LOW BIRTH WEIGHT NEONATES

1.4.1 SKIN

Chlorhexidine has been used for decades as a key part of routine care for newborn babies, including premature and low birth weight babies, and for invasive procedures.¹³ Indeed, as above, chlorhexidine is also on the WHO Essential Medicines list for cord care for prevention of neonatal mortality. The main potential safety issues related to chlorhexidine have been raised predominantly in extremely premature and low birth weight newborn babies (especially <1kg and <28 weeks)²⁷ where there have been some skin reactions, particularly when chlorhexidine is combined with alcohol and more rarely with water based chlorhexidine. The risk of skin damage is very low and has been associated with using larger quantities of chlorhexidine, particularly if it is allowed to pool in contact with the skin.^{27–30}

In this trial the risks will be minimised by the following aspects of the design:

- Excluding the babies at the highest risk (<1kg and <28 weeks)
- Using chlorhexidine without alcohol, delaying the start until after 24 hrs of life
- Strict operating procedures to prevent the risk of skin damage from pooling of liquid
- Close observation using a skin score assessment based on previous studies^{26,31} but including assessment of the full range of conditions associated with chlorhexidine and emollient
- Early discontinuation of chlorhexidine with signs of skin damage.

When chlorhexidine has been used in numerous previous studies including similar populations of babies, skin damage has been very rare.^{14,19,21,32,33}

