5.2.1.3 Stopping Chlorhexidine Early (Permanent Discontinuation)

Stopping chlorhexidine permanently before discharge/day 14 will be decided by the clinician. Possible reasons for permanent discontinuation would include the baby developing neurological symptoms such as focal neurological abnormalities, seizures or encephalopathy.

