10.2 ETHICAL CONDUCT

10.2.1 ETHICAL CONSIDERATIONS

The main ethical concern in this trial relates to potential skin damage, which could lead to infection, and potentially to scarring of the skin. Chlorhexidine is widely used for skin disinfection in neonates. The main risk is with high concentrations (>2%) in extremely low birth weight/preterm neonates (<1kg/<28 weeks), among whom skin reactions have been observed, particularly when chlorhexidine is combined with alcohol. The MHRA accordingly warns about use of high concentrations in this group. Hypothermia has also been observed after skin cleansing with chlorhexidine on the first day of life. This trial will exclude neonates less than 1kg at enrolment and below 28 weeks' gestational age, and start application 1-6 days after birth, which will minimise, although not entirely eradicate these risks. However, close and regular monitoring of the skin with a standardised skin condition scoring system, and temperature checking after application will allow chlorhexidine to be discontinued at the discretion of the local clinician.

Neurotoxicity, which is a theoretical concern, has never been reported in neonates despite widespread use of chlorhexidine, and large studies including daily application of chlorhexidine 4% to the cord, which has been associated with higher blood levels of chlorhexidine than skin application.

Given the absence of known toxicity even in the context of detectable blood chlorhexidine levels, this trial will follow other previous large studies in not measuring blood levels, but will assess neonates for any clinical signs of neurological disturbance (see Appendix II).

Importantly, safety concerns are one the main justifications for this pilot, in order to identify the safest but most effective regimen which could be tested in a larger trial aiming to reduce neonatal sepsis and mortality.

Confidentiality of the babies and their parents/care-givers will be maintained throughout the trial. Data submitted on CRFs/worksheets to trial sites and CTU, will be identified only by the trial number and date of birth (including random check letters to improve accuracy of identification). Date of birth is essential given all participants will be under 1 month of age.

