APPENDIX I SKIN SCORE ASSESSMENT

Skin toxicity score

Adapted from Lund & Osborne.³¹ The skin should be scored on each of the three domains (dryness, erythema and skin breakdown), and then the total score is the sum of the three components (minimum score 0, maximum score 12).

Highest grade from:

Grade 1 = Score of \geq 1 in \geq 2 categories

Grade 2 = Score of \geq 2 in \geq 2 categories

Grade 3 = Score of \geq 3 in \geq 2 categories

Grade 4 = Score of \geq 4 in \geq 2 categories

Score	Description
Domain 1	Dryness
0	Normal
1	Dry skin +/- scaling <50%
2	Dry skin + scaling >50% +/- cracking/fissures <50%
3	Very dry + cracking / fissures >50%
4	Very dry + cracking / fissures >75%
Domain 2	Erythema
0	Normal
1	Erythema <25%
2	Erythema 25-50%
3	Severe Erythema 50-75%
4	Severe Erythema >75%
Domain 3	Skin breakdown
0	Normal
1	Skin breakdown/ulceration/vesicles <5%
2	Skin breakdown/ulceration/vesicles 5-25%
3	Skin breakdown/ulceration/vesicles 25-50%
4	Skin breakdown/ulceration/vesicles >50%

Figure 3: Skin Affected Area assessment

Modified Lund and Browder chart for estimation of BSA burn involvement in infants and children. (From Harwood-Nuss A, Wolfson A, Linden C. *The clinical practice of emergency medicine*. Philadelphia: Lippincott-Raven; 1996:1207⁴⁰

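### For skin breakdown, the only scored prompt to consider stopping chlorhexidine is first met at 25-50%, which is late for the early-stopping safeguard in Protocol 1.4.1

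*Protocol*

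**What the plan says.** Protocol 5.2.1.2 lists three circumstances in which temporary or permanent discontinuation of chlorhexidine should be considered, at the treating clinician's discretion: temperature below 36.0C, neurological disturbance, and "Skin score >2 in any category immediately before chlorhexidine application". After a temporary stop the baby is reassessed at the next scheduled application and "the clinician will determine whether it should be restarted".

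Appendix I scores dryness, erythema and skin breakdown from 0 to 4 each. For breakdown, score 1 is below 5%, score 2 reads "Skin breakdown/ulceration/vesicles 5-25" per cent, score 3 reads "Skin breakdown/ulceration/vesicles 25-50" per cent, and score 4 is above 50%. Every toxicity grade requires a score in at least two domains.

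Section 1.4.1 gives, among the design features that minimise risk, "Early discontinuation of chlorhexidine with signs of skin damage". Section 10.2.1 states: "The main ethical concern in this trial relates to potential skin damage, which could lead to infection". The lay summary adds that applying an antiseptic "can sometimes cause skin reactions which may make it easier for bacteria to get into the babies instead of protecting them".

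**The concern.** Section 1.4.1 presents early stopping as part of the case that the trial is safe, and 5.2.1.2 is the only place in the protocol that attaches a skin score to that safeguard. In the breakdown domain that score is reached only at the third of four steps. A baby of 1-2 kg with ulcerated or vesicular skin in the 5-25% band can be scored just before a whole-body application and meet no numeric prompt to reconsider it.

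Broken skin is the harm that works most directly against the trial's purpose, because it may let bacteria in. A written number also tends to anchor practice: staff who read a limit above 2 may take a score of 2 as acceptable for continuing.

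**Working it through.** **Step 1. Map the prompt onto the scale.** Scores are whole numbers from 0 to 4, so above 2 means 3 or 4. First triggering level by domain (Appendix I):

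| Domain | Score 2 (no prompt) | Score 3 (prompt starts) |
|---|---|---|
| Dryness | scaling over 50%, with or without fissures under 50% | cracking or fissures over 50% |
| Erythema | 25-50% | 50-75% |
| Breakdown | 5-25% | 25-50% |

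**Step 2. Compare with the other measured prompt in the list.** Section 6.3 gives hypothermia Grade 1 as 35.5 to 36.0C. A prompt below 36.0C is therefore met within the mildest grade. The scales differ in kind, so this is only indicative, but one prompt starts at the first of four levels and the other at the third.

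**Step 3. Check whether the Appendix I grade fills the gap.** Take dryness 0, erythema 0, breakdown 2. Grade 1 needs a score of at least 1 in at least two domains, and only one domain scores. The pattern is ungraded as well as unprompted.

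**Step 4. Count the score patterns affected.**
- All patterns: 5 × 5 × 5 = 125.
- Prompted now (any domain above 2): 125 − 3 × 3 × 3 = 98.
- Prompted if breakdown counts from 2 and the other domains stay above 2: 125 − 3 × 3 × 2 = 107, so 9 are added.
- Those 9 all have breakdown 2 with dryness and erythema 0-2, and totals of 2 to 6 out of 12. One is ungraded (0,0,2), three are grade 1, and five are grade 2.
- Prompted if every domain counted from 2: 125 − 2 × 2 × 2 = 117, so 19 would be added. The narrower change spares 19 − 9 = 10 patterns of dryness or erythema alone.

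These are counts of patterns, not frequencies.

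**Step 5. Babies affected.** Section 9.3 gives 14 blocks, each with 12 active arms and one control: 14 × 12 = 168 active babies. The protocol gives no rate of breakdown at score 2 and describes skin damage as very rare. Let r be the assumed share of active babies who ever score 2 for breakdown without already meeting the present prompt.

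| Assumed r | Babies, 168 × r | Chance of at least one, 1 − (1 − r)^168 |
|---|---|---|
| 0.1% | 0.17 | 15% |
| 1% | 1.7 | 82% |
| 5% | 8.4 | over 99% |

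**Step 6. Worst-case effect on the bacterial-load comparison.** Suppose r applies in the 2% group only, every prompt leads to a permanent stop, and each stopped baby loses the whole 2 SD effect, the larger of the two cited in 9.3. The shift in the group mean is r × 2 SD = 0.002, 0.02 or 0.10 SD. Against the 0.66 SD that 9.3 states as detectable between concentrations (taken as stated), that is 0.3%, 3% or 15%. A discretionary prompt with restart would cost less.

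**The case against.** The strongest reply is that the protocol already covers this range. Section 1.4.1 speaks of signs of skin damage with no minimum score and can be read as a standing instruction. Section 5.2.1.3 says "Stopping chlorhexidine permanently before discharge/day 14 will be decided by the clinician", and 5.5 lists unacceptable toxicity or an adverse event as a reason to stop. Section 10.2.1 leaves discontinuation to the local clinician, and 1.4.5 commits the trial to use with care and monitoring of the skin. Section 5.2.2.3 goes further: if it is unclear which product caused a reaction, both are stopped. That applies in 6 of the 12 active arms, 84 of 168 babies. Skin is scored before each application and checked 30 minutes after, so a score of 2 should not go unseen. The skin-damage procedures in 7.1.3 may also set an earlier prompt. All of this stands, and it limits the point to the number in 5.2.1.2.

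A second reply is that score 2 is itself a choice, since breakdown below 5% is also a sign of damage. That is fair: the protocol does not say at what extent to pause. Section 3.2 does treat a score of 2 in any domain as poor skin condition at entry, so level 2 has some footing in the document.

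A third reply is that earlier interruption acts on the skin score, a co-primary outcome. This also stands. Lower exposure in babies whose skin reacts could slightly narrow later differences between concentrations, and the protocol gives no data to quantify it.

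A reader might infer more than the text supports. It does not follow that a clinician must continue at 5-25% breakdown, since several sections permit stopping. Nor does the stricter entry limit in 3.2 contradict 5.2.1.2, because an entry criterion and an on-treatment prompt can reasonably differ. Whether the limit was meant to read 2 or more cannot be settled from the document.

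**Conclusion.** The point holds as a late numeric prompt in one domain. The mapping from the limit in 5.2.1.2 to 25-50% breakdown is exact. That this is late is a judgement, supported by the safeguard in 1.4.1 and by the earlier hypothermia prompt in the same list. Dryness and erythema at score 2 are not at issue.

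The size is small: one score step, 9 further score patterns of 125, and between less than one baby and about eight at the assumed rates. Skin damage is described as very rare, so the low end may be nearer. The intention-to-treat comparison is unaffected by the present wording. The conclusion would weaken further if the procedures under 7.1.3 already prompt review at score 2; in that case the bullet should simply be aligned with them. This is a cheap improvement that the sponsor could make, not a flaw that threatens the trial.

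**What to change.** Replace the second bullet of 5.2.1.2 with: *Skin score >2 in the dryness or erythema domain, or 2 or more in the skin breakdown domain, immediately before chlorhexidine application (see Appendix I).* Keep it a prompt at the clinician's discretion, with the existing reassessment at the next scheduled application. Sections 5.2.2 and 5.2.2.3 need no change.

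The cost is one bullet and one line of site training. No new data are needed, because all three domains are already scored before each application. The score that triggers the prompt is recorded before any stop, so it stays in the safety outcome. The remaining downside is the possible slight narrowing of later skin-score differences.

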5.2.1.3 Stopping Chlorhexidine Early (Permanent Discontinuation)

Stopping chlorhexidine permanently before discharge/day 14 will be decided by the clinician. Possible reasons for permanent discontinuation would include the baby developing neurological symptoms such as focal neurological abnormalities, seizures or encephalopathy.

5.2.1.4 Handling Cases of Overdose

Overdose of chlorhexidine skin application has not been previously defined. For the purposes of this study, overdose will be defined as more than once daily application; any additional doses given will be recorded on the treatment CRF/worksheet. Adverse reactions to this would be expected to be similar to those already described in **Section 7.1.12** and will be recorded and reported in the same way as other adverse reactions (see **Section 7**).

5.2.1.5 Accountability & Unused Products

The diluted chlorhexidine to be used for the trial will be stored separately from routine supplies in a designated section of the pharmacy, the ward or other appropriate location. The product will be designated for strict use for trial participants. The designated trial pharmacist or nurse will confirm receipt of supplies prior to the commencement of the trial. Inventories will be conducted regularly, and logs returned to the main pharmacy as detailed in the MOP. Inventories will be in compliance with applicable local regulation, GCP and the protocol.

On no account should any product assigned to a baby be used for anyone else. Unused trial product must be returned to the main pharmacy if a baby is withdrawn from treatment before completing their randomised duration of therapy or if there is any remaining product.

At each site, a named person (pharmacist or research nurse) will be required to maintain complete records of all trial medication dispensed and returned. The designated pharmacist/nurse will, on receipt of supplies prior to the start of the trial, conduct an inventory and complete a receipt.

Procedures for product distribution, labelling, accountability and destruction will be detailed in the Pharmacy MOP. Product accountability will be regularly monitored and the remaining stocks checked against the amounts dispensed. At the end of the trial, all remaining products will be destroyed.

5.2.1.6 Compliance and Adherence

Each application of chlorhexidine will be given in hospital and recorded in the appropriate CRFs/worksheets.

5.2.2 EMOLLIENT

Sunflower oil will be used as emollient. Babies will be randomised to receive or not receive emollient together with chlorhexidine, to be applied daily or on alternate days (working days only) until day 14 of the trial or discharge from hospital, whichever is earlier.

Emollient should be applied after chlorhexidine is applied as described above. Approximately four grams per kilogram of body weight of emollient will be applied to the body (excluding face, ears and eyes) when the skin has become dry after application of chlorhexidine. After both products have been applied, the baby should be re-dressed and body temperature should be measured after 15 minutes. The baby should be observed for skin reactions at 30 minutes after application.

If chlorhexidine is being omitted for any reason, the emollient should normally still be applied as per protocol, at the discretion of the treating clinician.

5.2.2.1 Dispensing

Emollient will be prepared centrally in pharmacy and aliquoted, in aseptic conditions, into individual containers. Each baby will be allocated their own labelled bottle of emollient and they will not be shared between participants.

5.2.2.2 Dose Interruptions & Discontinuations

Doses will not be modified after the baby has been randomised. Consideration of temporary or permanent discontinuation of emollient should be made at the discretion of the treating clinician.

5.2.2.3 Stopping Emollient Early

If the clinician judges that an adverse reaction is likely to be related to emollient use, rather than to chlorhexidine, then the emollient may be stopped. Otherwise, if it is unclear which product is likely to be related to the adverse reaction, both products will be stopped.

5.2.2.4 Handling Cases of Overdose

Overdose will be defined as more than once daily application of emollient, and will be recorded on the treatment CRF/worksheet. This is unlikely to cause adverse reactions, as more frequent application of sunflower oil has been shown to be safe (e.g. three times daily application in one trial).²⁶ Any adverse reactions will be recorded as other adverse reactions.

5.2.2.5 Accountability & Unused Emollient

Unused emollient which has already been assigned to a specific individual baby will be discarded without being used for other babies or trial participants. See **Section 5.2.1.5** above for general accountability.

5.2.2.6 Compliance & Adherence

Each application of emollient will be given in hospital and recorded in the CRFs/worksheets.

5.3 CONTROL GROUP

5.3.1 PRODUCTS

The control group will receive routine clinical care. Any skin product which is used will be recorded on CRFs/worksheets, along with the indication for its use.

The control group will receive assessments on alternate working days, including skin score, AE and temperature assessments, as well as swabs being taken on the protocol schedule.

